9.10.7. Clinical Laboratory Tests

Refer to [Table 6](#) for the list of clinical laboratory tests to be performed and the Schedules of Assessments ([Table 7](#) and [Table 8](#)) for timing and frequency for each test. Details regarding clinical laboratory sample collection, preparation, and shipment are provided in the Laboratory Manual by the central laboratory.

Clinical safety laboratory tests should be completed pre-dose. The Investigator must review the laboratory report, document this review, and record any clinically relevant changes occurring during the study in the adverse event section of the eCRF (results of the total WBC and ALC will be reviewed and monitored as described in Section [9.8.4](#)). The laboratory reports must be filed with the source documents. Clinically significant abnormal laboratory findings are those that are not associated with the underlying disease, unless judged by the Investigator to be more severe than expected for the subject's condition.

All laboratory tests with values considered clinically significantly abnormal during participation in the study or within 30 days after the last dose of study treatment should be repeated until the values return to normal or baseline or are no longer considered clinically significant by the Investigator or Medical Monitor.

- If such values do not return to normal/baseline within a period of time judged reasonable by the Investigator, the etiology should be identified, and the Sponsor should be notified.
- All protocol-required laboratory assessments, as defined in the Schedules of Assessments ([Table 7](#) and [Table 8](#)), must be conducted in accordance with the Laboratory Manual.
- If laboratory values from non-protocol-specified laboratory assessments performed at the institution's local laboratory require a change in subject management or are considered clinically significant by the Investigator (eg, adverse event, SAE, or dose modification), then the results must be recorded in the eCRF.

For guidance on monitoring subjects with notable lymphopenia, please refer to Section [9.8.4](#).

Table 6: Clinical Laboratory Tests

| | | |
|--------------------------------------------------------------------------------------------------------------------------------------------------|----------------------------|-----------------------------|
| SCREENING Only | | |
| Virology | | |
| HIV, HBsAg, HCV (RIBA) | | |
| Stool Sample | | |
| Bacterial culture, ova and parasites, C. difficile | | |
| Drugs of Abuse | | |
| Amphetamine, barbiturates, benzodiazepines, cocaine, methadone, methamphetamine, methylenedioxymethamphetamine, opiate, oxycodone, phencyclidine | | |
| Others | | |
| Hemoglobin A1C, QuantiFERON | | |
| PREGNANCY TESTING | | |
| Serum pregnancy test human beta-chorionic gonadotropin (β -hCG) - Screening | | |
| Urine β -hCG (only for women of childbearing potential) | | |
| CLINICAL CHEMISTRY, HEMATOLOGY, AND COAGULATION | | |
| Hematology | Serum Chemistry | |
| Hematocrit | Albumin | Potassium |
| Hemoglobin | Alkaline phosphatase | Sodium |
| Mean corpuscular hemoglobin | Alanine aminotransferase | Thyroid-stimulating hormone |
| Mean corpuscular hemoglobin concentration | Aspartate aminotransferase | Thyroxine free |
| Mean corpuscular volume | Bicarbonate | Total bilirubin |
| Platelet count | Blood urea nitrogen | Triiodothyronine free |
| Red blood cell count | C-reactive protein | Total cholesterol |
| White blood cell count with differential ^a | Calcium | Total protein |
| TBNK ^a | Chloride | Triglycerides |
| | Creatinine | Uric acid |
| | Creatine kinase | |
| | Direct bilirubin | |
| Coagulation | Glucose | |
| Prothrombin time | Gamma-glutamyl transferase | |
| Activated partial thromboplastin time | Lactate dehydrogenase | |
| International normalized ratio | Phosphorus | |
| URINALYSIS | | |
| Appearance | Nitrite | |
| Bilirubin | Occult blood | |
| Color | pH | |
| Glucose | Protein | |
| Ketones | Specific gravity | |
| Microscopic examination of sediment | Urobilinogen | |

Table 6: Clinical Laboratory Tests (Continued)

| |
|----------------------------------------------------------------------------------------------------------------------------------------------------------------------------------------------------|
| 
BIOMARKERS Lymphocytes^{a,b} hs-CRP^b Fecal calprotectin^b Immunophenotyping Proteomics RNA Transcriptomics Fecal microbiome
 |
| 
GENETICS Genomic DNA (optional)
 |
| 
STOOL SAMPLE^c Ova and parasites, C. difficile
 |

^a Total WBC, neutrophil, lymphocyte, and TBNK will be available for review prior to randomization. After randomization, the total WBC, neutrophil, lymphocyte, and CD4 T cell counts will be reviewed by an unblinded Medical Monitor who will provide instructions to the site investigator in the event of significant lymphopenia. Investigators will remain blinded to the results after randomization. Refer to Section 9.8.4 for additional details.

^b Investigators will remain blinded to the results after randomization.

^c Stool sample for bacterial culture, ova, and parasite evaluation, and *C. difficile* assay at any point in the study when a subject becomes symptomatic, including worsening or return of disease activity.

β-hCG, human beta-human chorionic gonadotropin; HBsAg, hepatitis B surface antigen; HCV, hepatitis C virus; HIV, human immunodeficiency virus; hs-CRP, high-sensitivity C-reactive protein; IgG, immunoglobulin G; RIBA, recombinant immunoblot assay; TBNK, T lymphocytes, B lymphocytes, and natural killer lymphocytes; WBC, white blood cells

9.10.7.1. Screening

9.10.7.1.1. Drugs of Abuse

A standard urine drug screen will be performed (Table 6). Subjects who test positive will be assessed for eligibility for study participation by the Investigator.

9.10.7.1.2. Pregnancy Testing

A serum pregnancy test for β-hCG will be performed on women of childbearing potential to determine eligibility. Post-screening urine pregnancy tests (β-hCG) should be performed as indicated in the Schedules of Assessments (Table 7 and Table 8). A monthly home pregnancy test in non-visit months should be performed in countries where allowed per local regulation and any positive result immediately reported to the study site. If not allowed per local regulations, this pregnancy test will be performed on site during an unscheduled visit. If at any point there is a case of a positive urine β-hCG test, the subject will have study treatment interrupted and a serum sample submitted to the central laboratory for β-hCG testing. If the serum test confirms positive, the subject will be withdrawn from the study treatment and all the necessary follow-up assessments will be conducted as per Section 9.10.9. If the serum test is negative, the subject may resume study treatment.

Negative pregnancy test results must be documented for all women of childbearing potential prior to dosing at applicable study visits. Women who are surgically sterile or who are postmenopausal are not considered to be of childbearing potential. Postmenopausal is defined as 12 consecutive months with no menses without an alternative medical cause.

9.10.7.1.3. Virology

Screening HIV antibody, hepatitis B (ie, HBsAg), and HCV (recombinant immunoblot assay, if positive HCV RNA should be used to confirm infection).

9.10.7.2. Clinical Chemistry, Hematology, Coagulation, and Urinalysis

Clinical chemistry, hematology, coagulation, and urinalysis parameters that will be assessed during the study are identified in [Table 6](#).

Subjects will be in a seated or supine position during blood collection. All laboratory samples should be collected prior to the administration of study treatment at applicable visits (Refer to [Section 9.6](#) for timing of blood draws for PK).

9.10.8. Adverse Events

9.10.8.1. Definitions

9.10.8.1.1. Adverse Event

An adverse event is any untoward medical occurrence in a subject or clinical investigational subject administered a medicinal product and which does not necessarily have a causal relationship with this treatment. An adverse event can therefore be any unfavorable and unintended sign, symptom, or disease temporally associated with the use of a medicinal product, whether or not considered related to the medicinal product.

Adverse events can be any of the following:

- Unfavorable changes in general condition
- Subjective or objective signs/symptoms
- Concomitant disease or accidents
- Clinically relevant adverse changes in laboratory parameters over the course of the study
- Preexisting conditions that worsen in severity, increase in frequency, or have new signs/symptoms

9.10.8.1.2. Serious Adverse Event

An adverse event should be classified as an SAE if it meets one of the following criteria:

| | |
|-------------------|---------------------------------------------------------------------------------------------------------------------------------------------------------------------------------------|
| Fatal: | Adverse event resulted in death. |
| Life-threatening: | The adverse event placed the subject at immediate risk of death. This classification does not apply to an adverse event that hypothetically might cause death if it were more severe. |

| | |
|----------------------------------------|-----------------------------------------------------------------------------------------------------------------------------------------------------------------------------------------------------------------------------------------------------------------------------------------|
| Hospitalization: | The adverse event required or prolonged an existing inpatient hospitalization. Hospitalizations for elective medical or surgical procedures or treatments planned before the signing of informed consent in the study or routine check-ups are not SAEs by this definition. |
| Disabling/ incapacitating: | The adverse event resulted in a persistent or significant incapacity or substantial disruption of the subject's ability to conduct normal life functions. |
| Congenital anomaly or birth defect: | An adverse outcome in a child or fetus of a subject exposed to the molecule or study treatment regimen before conception or during pregnancy. |
| Medically significant: | The adverse event did not meet any of the above criteria but could have jeopardized the subject and might have required medical or surgical intervention to prevent one of the outcomes listed above or involves suspected transmission via a medicinal product of an infectious agent. |

9.10.8.1.3. Adverse Drug Reaction

An adverse drug reaction (ADR) in the pre-approval clinical experience with a new medicinal product or its new usages, particularly as the therapeutic dose(s) may not be established, is any noxious and unintended response to a medicinal product related to any dose. The phrase "responses to a medicinal product" means that a causal relationship between a medicinal product and an adverse event is at least a reasonable possibility (ie, the relationship cannot be ruled out).

9.10.8.1.4. Adverse Events of Special Interest

Based on the mechanism of action of etrasimod and prior experience with other agents acting via a similar mechanism, potential adverse events of special interest may be identified. In addition to appropriate reporting of these events as an adverse event or SAE, supplementary detailed information may be collected.

If there are any signs of progressive multifocal leukoencephalopathy (PML)-related symptoms, the Investigator should withhold study treatment and perform appropriate diagnostic evaluation per local standard of care at the first signs suggestive of PML. Typical symptoms associated with PML are diverse, progress over days to weeks, and may include progressive weakness on one side of the body or clumsiness of limbs, disturbance of vision, and changes in thinking, memory, and orientation leading to confusion and personality changes. The Investigator must notify the Medical Monitor of such an event.

Guidance for the Assessment of Potential Progressive Multifocal Leukoencephalopathy is provided in [Appendix 5](#).

9.10.8.1.5. Severity

The severity of each adverse event will be assessed at the onset by a nurse/or physician. When recording the outcome of the adverse event the maximum severity of the adverse event experienced will also be recorded. The severity of each adverse event will be graded according to the Common Terminology Criteria for Adverse Events, version 5.0 (CTCAE v5.0):

- | | |
|----------|----------------------------------------------------------------------------------------------------------------------------------------------------------------------------------------------------------------------------------------------------------------------|
| Grade 1: | Mild; asymptomatic or mild symptoms; clinical or diagnostic observations only; intervention not indicated. |
| Grade 2: | Moderate; minimal, local or noninvasive intervention indicated; limiting age-appropriate instrumental activities of daily living (ADL). |
| Grade 3: | Severe or medically significant but not immediately life-threatening; hospitalization or prolongation of hospitalization indicated; disabling, limiting self-care ADL (eg, preparing meals, shopping for groceries or clothes, using the telephone, managing money). |
| Grade 4: | Life-threatening consequences, urgent intervention indicated. |
| Grade 5: | Death related to adverse event. |

9.10.8.1.6. Relationship

The Investigator (or designee) will make a determination of the causal relationship of the AE to the study drug using a 4-category system according to the following guidelines:

- | | |
|-------------------|------------------------------------------------------------------------------------------------------------------------------------------------------------------------------------------------------------------------------------------------------------------------|
| Not Related: | The AE is definitely caused by the subject's clinical state or the study procedure/conditions. |
| Unlikely Related: | The temporal association between the AE and the drug is such that the drug is not likely to have any reasonable association with the AE. |
| Probably Related: | The AE follows a reasonable temporal sequence from administration of the drug and cannot be reasonably explained by the known characteristics of the subject's clinical state, environmental, or toxic factors, or other modes of therapy administered to the subject. |
| Related: | The AE follows a reasonable temporal sequence from administration of the drug, abates upon discontinuation of the drug, follows a known or hypothesized cause-effect relationship, and (if appropriate) reappears when the drug is reintroduced. |

The Investigator will use clinical judgment to determine the relationship. Alternative causes, such as underlying disease(s), concomitant therapy, and other risk factors, as well as the temporal relationship of the event to the study treatment administration should be considered and investigated. The Investigator should consult the IB and the Product Information of marketed products within the drug class, when applicable. For each adverse event/SAE, the Investigator must document in the medical notes that he/she has reviewed the adverse event/SAE and has provided an assessment of causality. There may be situations in which an SAE has occurred and

the Investigator has minimal information to include in the initial report to the Sponsor; however, it is very important that the Investigator always make an initial assessment of causality for every event before the initial transmission of the SAE to the Sponsor. The Investigator may change his/her opinion of causality based on subsequent receipt of information and send an SAE follow-up report with the updated causality assessment. The causality assessment is one of the criteria used when determining regulatory reporting requirements.

9.10.8.2. Eliciting and Recording Adverse Events

9.10.8.2.1. Eliciting Adverse Events

Subjects will be instructed that they may report adverse events at any time. An open-ended or nondirected method of questioning should be used at each study visit to elicit the reporting of adverse events.

9.10.8.2.2. Recording Adverse Events

The adverse event reporting period for safety surveillance begins when the subject is initially included in the study (date of first signature of informed consent) and continues up to 30 days after the last administration of study treatment. If an adverse event is not resolved or stabilized by this time, the Sponsor in consultation with the Investigator will decide whether to continue to monitor the adverse event or closeout the event in the database if no further follow-up is necessary.

Any SAE suspected to be related to the study treatment must be reported whenever it occurs, irrespective of the time elapsed since the last administration of study treatment.

Investigators and study personnel will record all adverse events and SAEs whether received through an unsolicited report by a subject, elicited during subject questioning, discovered during physical examination, laboratory testing, and/or other means by recording them on the eCRF and/or SAE Form, as appropriate. The following information should be recorded on the adverse event eCRF:

- Description including onset and resolution dates
- Whether it met SAE criteria
- Severity
- Relationship to study treatment or other causality
- Outcome

For SAEs, events occurring secondary to the primary event should be described on the eCRF in the narrative description field.

The following should be considered when recording SAEs:

- Death is an outcome of an event. The event that resulted in the death should be recorded and reported on the eCRF.
- For hospitalizations, surgical, or diagnostic procedures, the illness leading to the surgical or diagnostic procedure should be recorded as the SAE, not the procedure

itself. The procedure should be captured in the narrative as part of the action taken in response to the illness.

9.10.8.2.3. Diagnosis Versus Signs or Symptoms

In general, the use of a unifying diagnosis is preferred to the listing out of individual symptoms. Grouping of symptoms into a diagnosis should only be done if each component sign and/or symptom is a medically confirmed component of a diagnosis as evidenced by standard medical textbooks. If any aspect of a sign or symptom does not fit into a classic pattern of the diagnosis, report the individual symptom as a separate adverse event.

9.10.8.3. Reporting Adverse Events

All SAEs are subject to reporting requirements.

9.10.8.3.1. Serious Adverse Events

Any adverse event considered serious by the Investigator or Sub-investigator or that meets serious criteria should be reported to the designated safety contact **within 24 hours of becoming aware of the event (or in India within 24 hours of event occurrence)**. Enter the SAE information into eCRF, and send other available pertinent information (eg, hospital records, laboratory results, etc) to the designated Sponsor Contact.

IQVIA Pharmacovigilance

[REDACTED]

[REDACTED]

[REDACTED]

If additional information is required or becomes available for a previously reported SAE, entry of the new information into eCRF should be completed **within 24 hours of awareness**.

Elective hospitalization and/or surgery for clearly preexisting conditions (eg, a surgery that has been scheduled prior to the subject's entry into the study) will not be reported as an SAE.

Any SAE that is ongoing when the subject completes the study or discontinues the study will be followed by the Investigator until the event resolved, stabilized or returned to baseline status.

9.10.8.3.2. Serious, Unexpected Adverse Drug Reactions

All ADRs that are both serious and unexpected are subject to expedited reporting to regulatory agencies. An unexpected ADR is one for which the nature or severity is not consistent with information in the relevant source documents.

Since etrasimod is an investigational medicinal product that has not yet been approved for marketing in any country, the IB in effect during the study will serve as the Reference Safety Information for determining whether an AE is expected or unexpected.

9.10.9. Pregnancy

If at any point a serum β -hCG pregnancy test is positive, the subject will be withdrawn from the study treatment.

Details of all pregnancies in female subjects and female partners of male subjects will be collected after the start of study treatment and until 30 days after the last dose.

Pregnancy (during maternal or paternal exposure to study treatment) does not meet the definition of an adverse event; however, to fulfill regulatory requirements, any pregnancy and/or pregnancy outcome should be reported via the Pregnancy Report Form to the designated Sponsor Contact **within 24 hours of awareness** to collect data on the pregnancy and on the outcome for both the mother and the fetus.

Abnormal pregnancy outcomes (eg, spontaneous abortion, fetal death, stillbirth, congenital anomalies, ectopic pregnancy) are considered SAEs and should be reported as such (following the SAE reporting process) even if outside the SAE reporting period.

9.11. Procedures for Overdose

The current edition of the IB should be referenced for overdose procedures.

There is no established overdose threshold for this clinical study, nor is there any recommended specific treatment for an overdose but to provide supportive care if clinically indicated.

In the event of a suspected overdose, the Investigator and/or treating physician should:

1. Closely monitor the subject for any AE/SAE and laboratory abnormalities and follow the AE reporting process, including contacting the Medical Monitor.
2. Obtain a plasma sample for PK analysis within 7 days from the date of the last dose of study treatment, if possible, and if requested by the Medical Monitor.
3. Document the total quantity of the excess dose, taking into consideration the duration of the overdose in the eCRF and the time frame.

Subjects who overdose will be counseled on correct dosing and administration of study treatment. Decisions regarding study discontinuation, dose interruptions, or dose modifications will be made by the Investigator in consultation with the Medical Monitor based on the clinical evaluation of the subject.

10. PLANNED STATISTICAL METHODS

10.1. General Considerations

All individual subject data for all randomized subjects will be presented in data listings. All efficacy and safety endpoints will be summarized by treatment group. Full details of the statistical considerations and planned analyses will be described in the study Statistical Analysis Plan (SAP).

10.2. Determination of Sample Size

Based on a 2-group Fisher's exact test, a 1-sided significance level of 0.025, and a 2:1 randomization ratio, 420 total subjects (280 etrasimod, 140 placebo) are required to achieve 93.4% power to detect a difference of 13.5% in the primary endpoint of clinical remission at Week 52 between the etrasimod treatment group (23.5%) and the placebo treatment group

(10.0%). With this sample size, there will be 96% power to detect a difference of 12.5% in the other primary endpoint of clinical remission at Week 12, assuming a placebo rate at 6.0%. The lower bound of overall power for both primary endpoints (as coprimary endpoints) is at least 90%; and since the two primary endpoints are expected to be at least moderately positively correlated, the actual overall power to reject both of their null hypotheses is likely to be greater than 90%.

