The overall rationale for this amendment is to update the subject enrollment number and include guidance for conducting virtual and offsite visits. Also, information on anti-arrhythmic drugs was added to prohibited concomitant therapies and the corticosteroid-free remission secondary endpoint was updated. Language was updated regarding timing of screening optical coherence tomography (OCTs) and pulmonary function tests (PFTs). Additionally, an exclusion criterion was added regarding treatment with topical rectal Chinese medicine, enemas or suppositories prior to randomization. Minor corrections were made for consistency within the protocol.

Summary of Changes

| Section No. and Name | Description of Change | Brief Rationale |
|---------------------------------------------------------------------------------------------------------------------------------------------------------------------------|----------------------------------------------------------------------------------------------------------------------------------------------------------------------------------------------------------------|-----------------------------------------------------------------------------------------------------------------------------------------------------------------------------------------------------|
| Throughout | Minor editorial, formatting, and nomenclature revisions | Minor and do not affect the conduct of the protocol; therefore, have not been summarized |
| Title Page | Updated Amendment 4.0; Version date: 22 December 2020 | Administrative change |
| Title Page Appendix 7, Sponsor Signature | Revised Sponsor’s Responsible Medical Officer name and title to  | Administrative change |
| Protocol History | Updated protocol history table | Administrative change |
| Protocol Synopsis: Number of subjects (planned) Protocol Synopsis: Statistical Methods 3.1. Summary of Study Design, Figure 1 10.2. Determination of Sample Size | Updated to enrollment to 420 subjects | To increase the joint statistical power of the co-primary endpoints to at least 90% and enable a more robust assessment in the per protocol analysis due to anticipated impact by COVID-19 pandemic |

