7. DETERMINATION OF SAMPLE SIZE

Based on a 2-group Fisher’s exact test, a 1-sided significance level of 0.025, and a 2:1 randomization ratio, 420 total subjects (280 etrasimod, 140 placebo) are required to achieve 93.4% power to detect a difference of 13.5% in the primary endpoint of clinical remission at Week 52 between the etrasimod treatment group (23.5%) and the placebo treatment group (10.0%). With this sample size, there will be 96% power to detect a difference of 12.5% in the other primary endpoint of clinical remission at Week 12, assuming a placebo rate at 6.0%. The lower bound of overall power for both primary endpoints (as coprimary endpoints), is at least 90%; since the 2 primary endpoints are expected to be at least moderately, positively correlated, the actual overall power to reject both of their null hypotheses is likely to be greater than 90%. Workbook calculations from EAST® 6 statistical software are included below.

Design: Discrete Endpoint: Two-Sample Test - Parallel Design - Fisher's Exact

Test Parameters	
Design ID	Week 52 Clin Rem
Test Type	2-Sided
Specified α	0.05
Power	0.934
Sample Size (n)	420
Model Parameters	
Proportion Treatment (π_t)	0.235
Proportion Control (π_c)	0.1
$\delta = \pi_t - \pi_c$	
Under H0	0
Under H1	0.135
Allocation Ratio (n_t/n_c)	2

Sample Size Information

Sample Size (n)	420
Treatment (n _t)	280
Control (n _c)	140

Design: Discrete Endpoint: Two-Sample Test - Parallel Design - Fisher's Exact

Test Parameters	
Design ID	Week 12 Clin Rem
Test Type	2-Sided
Specified α	0.05
Power	0.96
Sample Size (n)	420
Model Parameters	
Proportion Treatment (π_t)	0.185
Proportion Control (π_c)	0.06
$\delta = \pi_t - \pi_c$	
Under H0	0
Under H1	0.125
Allocation Ratio (n_t/n_c)	2

⊖ **Sample Size Information**

Sample Size (n)	420
Treatment (n _t)	280
Control (n _c)	140

8. STATISTICAL CONSIDERATIONS**8.1. Multicenter Studies**

This study will be conducted by multiple investigators at multiple centers internationally. Randomization to treatment groups is stratified by:

- Naïve to biologic or JAK inhibitor therapy at study entry (Yes or No)
- Baseline corticosteroid use (Yes or No)
- Baseline disease activity (MMS: 4 to 6 or 7 to 9)

Data from all sites will be pooled and statistical analyses will not be adjusted for investigational site, country, or geographic region.

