16.1.3. Primary Analysis of Primary Efficacy Variables

The following hypotheses (H_{01} and H_{02}) for the coprimary endpoints will be tested:

H_{01} : The proportion of subjects achieving clinical remission at Week 12 is the same between etrasimod and placebo.

H_{11} : The proportion of subjects achieving clinical remission at Week 12 is different between etrasimod and placebo.

H_{02} : The proportion of subjects achieving clinical remission at Week 52 is the same between etrasimod and placebo.

H_{12} : The proportion of subjects achieving clinical remission at Week 52 is different between etrasimod and placebo.

Both hypotheses will be tested at the 2-sided α level, 0.05.

The primary efficacy analysis will be performed for the FAS with Baseline MMS 5 to 9. The Cochran-Mantel-Haenszel (CMH) test will be used, stratified by naïve to biologic or JAK inhibitor therapy at study entry (Yes or No), Baseline corticosteroid use (Yes or No), and Baseline disease activity (MMS: 4 to 6 or 7 to 9). Reported randomization stratum will be used in the model. Results will be expressed as the number and percentage of subjects in remission, difference in remission percentages and 95% CI and p-value, odds ratio and 95% CI. If there are no responders in both treatment groups in any stratum, the difference in remission percentages and associated inferences can still be made. However, the odds ratio and its CI may be calculated from the unstratified CMH.

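### The stated floor of at least 90% overall power does not follow from the two stated powers: 93.4% and 96% guarantee only 89.4%, and give 89.7% under independence

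*Protocol*

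**What the plan says.** Protocol 10.2 sizes the trial as follows: "Based on a 2-group Fisher's exact test, a 1-sided significance level of 0.025, and a 2:1 randomization ratio", with "420 total subjects (280 etrasimod, 140 placebo"). It gives 93.4% power for Week 52 clinical remission (23.5% versus 10.0%) and 96% for Week 12 (a 12.5-point difference over a 6.0% placebo rate). It then states: "The lower bound of overall power for both primary endpoints (as coprimary endpoints) is at least 90" per cent. Only after that does it add that the endpoints should be at least moderately positively correlated, so that actual overall power probably exceeds 90%.

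The synopsis repeats this paragraph. SAP Section 7 repeats the claim, "The lower bound of overall power for both primary endpoints (as coprimary endpoints), is at least 90" per cent, and adds that workbook calculations from the sizing software are shown. The printout lists a 2-sided Fisher test with alpha 0.05 for each endpoint.

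Protocol 10.12.1 and SAP 8.4 count the study as an overall success only if both primary null hypotheses are rejected. The Amendment 4.0 summary of changes gives the reasons for enrolling 420 as to "increase the joint statistical power of the co-primary endpoints to at least 90% and enable a more robust assessment" in the per-protocol analysis.

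**The concern.** A lower bound on joint power should hold without further assumptions, or should name the assumption it needs. Here 90% is offered as the floor first, and correlation is credited only in the next clause, as a reason to expect more. The floor therefore has to come from the two single-endpoint powers alone, and it does not.

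The figure matters because overall success, and access to the key secondary tests (Protocol 10.12.1), require both rejections. Joint power is thus the operative power of the trial. It is also one of the two reasons given for 420 subjects.

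A second, smaller point sits in the same paragraph. The text specifies "a 1-sided significance level of 0.025", while the SAP printout is 2-sided at 0.05. For Fisher's exact test with unequal groups these are not the same calculation, so a reader who checks the test named in the text cannot reproduce the printed powers.

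**Working it through.** **Inputs.** From Protocol 10.2 and the SAP Section 7 printout: 280 etrasimod and 140 placebo; Week 52 rates 23.5% and 10.0%; Week 12 rates 18.5% and 6.0% (6.0% + 12.5%); stated powers 93.4% and 96%.

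**Step 1: reproduce the stated powers.** Exact power of Fisher's test at 280/140, by enumerating all outcomes:

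| Test | Week 52 | Week 12 |
|---|---|---|
| Stated | 93.4% | 96% |
| Fisher, 2-sided 0.05 (SAP printout) | 93.44% | 95.98% |
| Fisher, 1-sided 0.025 (named in the text) | 92.76% | 95.55% |

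The 2-sided test reproduces both figures. The 1-sided test reproduces neither.

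**Step 2: joint power from the stated powers.**

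- Guaranteed minimum over all correlations: P52 + P12 - 1 = 0.934 + 0.96 - 1 = 0.894.
- Independence: P52 x P12 = 0.934 x 0.96 = 0.8966.

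The shortfalls against 90% are 0.6 and 0.3 points.

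**Step 3: does rounding explain it?** With the unrounded 2-sided Fisher powers, 0.9344 + 0.9598 - 1 = 0.8942 and 0.9344 x 0.9598 = 0.8969. It does not. The 1-sided test named in the text would give 88.3% and 88.6%.

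**Step 4: how much correlation would 90% need?** The documents give no value. Assuming bivariate normal test statistics with the stated powers:

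| Correlation | 0 | 0.1 | 0.2 | 0.3 | 0.5 | 0.7 |
|---|---|---|---|---|---|---|
| Joint power | 89.7% | 89.8% | 89.9% | 90.1% | 90.7% | 91.4% |

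The crossing is at about 0.23.

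**Step 5: the gap in subjects.** Same 2-sided Fisher calculation, 2:1 allocation:

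| N | Week 52 | Week 12 | Guaranteed minimum | Independence |
|---|---|---|---|---|
| 420 (280/140) | 93.44% | 95.98% | 89.42% | 89.69% |
| 423 (282/141) | 93.64% | 96.12% | 89.76% | 90.01% |
| 426 (284/142) | 93.82% | 96.25% | 90.07% | 90.31% |

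The independence figure passes 90% at 423 and the guaranteed minimum at 426.

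**Step 6: a test closer to the planned analysis.** The primary analysis is a stratified CMH test, not Fisher's. An unstratified Pearson test at 280/140 has exact powers of 94.16% and 96.42%, so the guaranteed minimum is 0.9416 + 0.9642 - 1 = 90.6%.

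**The case against.** The strongest reply is that this is trivial. The plan expects at least moderate positive correlation, for which 89.7% is the relevant floor, and that rounds to 90%. A correlation of about 0.23 is enough to reach 90%, and the Pearson calculation puts even the worst case at 90.6%. The three places are one sentence copied, not three errors. On this view the trial is adequately powered and the conclusion that actual power is probably above 90% is sound.

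Most of that stands, and it limits the finding to a misstated figure. It does not rescue the sentence. The text says both that this is a lower bound and that it is at least 90%, and it reports Week 52 power to a tenth of a point, so rounding upwards is not available. The Pearson result is not the calculation the text names or prints.

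On the label, it is fair to say that 1-sided 0.025 and 2-sided 0.05 are often treated as interchangeable, and that the printout and SAP 16.1.3 ("Both hypotheses will be tested at the 2-sided α level, 0.05") already show the 2-sided setting. The difference is still 0.4 to 0.7 points on the single powers, as large as the gap in the bound, so the label should match.

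Two limits also stand. The figure of 89.4% is a minimum over correlations, not the joint power at every correlation. And SAP 3.3 moves the primary analysis to subjects with Baseline MMS 5 to 9, while Section 7 still sizes on all 420. The corrected sentence would describe the sizing calculation, not the power of that smaller set.

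**Conclusion.** The concern holds. From 93.4% and 96%, the guaranteed joint power is 89.4%, and it is 89.7% if the endpoints are independent; the stated floor of at least 90% is wrong by 0.3 to 0.6 points. This rests only on the plan's own powers, which reproduce exactly for the 2-sided 0.05 Fisher test at 280/140. The statement that actual power is likely above 90% remains reasonable, subject to a correlation of about 0.23 or more between the test statistics under the bivariate normal assumption. The 1-sided 0.025 description of the sizing test is a wrong label and not evidence of lower power. The finding does not show that 420 subjects are too few.

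**What to change.** In Protocol 10.2, the synopsis and SAP Section 7, replace the sentence with: *overall power is at least 89.4% for any correlation and about 89.7% if the endpoints are independent; with the expected positive correlation it is likely to be about 90% or higher*. In the same paragraph, describe the sizing test as the 2-sided 0.05 Fisher exact test that the printout shows.

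The cost is one sentence and one label in each place, with no change to design, analysis, alpha or sample size. Protocol 11.2 sends protocol modifications to the ethics committee before implementation, so the protocol text can sensibly wait for an amendment made for other reasons, with the SAP and the clinical study report carrying the corrected figure meanwhile.
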